### 6.10 *Explant Evaluation*

The study Sponsor is committed to understanding the effects of the human *in vivo* environment on the stent graft over time. To this end, all explanted devices should be returned to the study Sponsor for evaluation by a Pathologist at an independent Explant Laboratory. Refer to **Appendix VI: Explant Procedure** for specific instructions for managing the removal, shipping, and handling of the explanted AAA device.

### 6.11 *Adverse Events*

An adverse event is any new, undesirable medical occurrence or change (worsening) of a pre-existing condition that occurs in a subject, whether or not considered to be associated with the product. Elective hospitalizations for pre-existing conditions (e.g., elective cosmetic procedures) are not adverse events. The following events are to be captured in this study:

- Adverse Events, regardless of device relationship
- Serious Adverse Events, regardless of device relationship
- All Deaths
- Unanticipated Adverse Device Effects

Requirements for reporting AEs are dependent upon the reviewing IRB/EC policy. Adverse events will be reviewed by a Clinical Events Committee (CEC). The CEC will meet periodically, a minimum of annually.

Adverse Event information is recorded in the **Adverse Event eCRF**.

For purposes of this study, the following events are not considered adverse events, because they are expected to occur in conjunction with the index procedure or are associated with subjects undergoing customary, standard of care endovascular AAA repair procedures:

- Early post-operative pain (within 24 hours of index procedure) at the access site and/or related to position on procedure table
- Post-anesthesia/conscious sedation emesis, nausea, or headache (within 24 hours of index procedure)
- Electrolyte imbalance without clinical sequelae following index procedure, even if requiring correction
- Low grade temperature increase (< 101.0 °F)
- Hematocrit decrease from baseline of less than 6 points (2 grams of hemoglobin) that remains above 30% and is not associated with hemodynamic changes and does not require transfusion
- Blood loss not requiring transfusion and not resulting in decreased hematocrit.

- Minor, localized tenderness, swelling, induration, bruising, erythema, hematoma etc. at vascular access site that does not require surgical intervention, evacuation, transfusion, or antibiotics
- Prophylactic administration of atropine
- Prophylactic pacing
- Isolated, non-sustained PVCs/PACs
- Non-sustained, arrhythmia not requiring treatment or intervention
- Hypotension or hypertension not requiring treatment or intervention
- Atelectasis not requiring treatment
- Prolonged hospitalization due to logistical delays relating to discharge to a skilled nursing facility, care facility, rehabilitation center, etc.

The Investigator and/or IRB/EC may require that these events are reported as adverse events. In this case, the Investigator should report these observations based on their medical judgment and requirements of the IRB/EC.

**Device-related adverse events should be reported to the study Sponsor as soon as possible (24 hours recommended), but no more than 10 working days after the date the site becomes aware of the event.**

Device-Related: Event is caused or contributed by any component of the device during delivery, deployment or while the device is in situ post-operatively

- “Caused or Contributed” means that an injury was or may have been attributed to the study device, or that the study device was or may have been a factor in an injury, including events occurring as a result of:
  - Any event resulting from intervention on the AAA or device
  - Any device failure, malfunction, inadequacy, including operator error

Procedure-Related: Event is caused or contributed by the initial study device implantation (index) procedure, up to 30 days, unless a different etiology can be identified

### **6.12 Serious Adverse Events (SAE)**

A serious adverse event (SAE) defined as one that suggests a significant hazard or side effect, regardless of the investigator or Sponsor’s opinion on the relationship to the investigational product. This includes, but may not be limited to, any event that:

- Is fatal
- Is life-threatening
- Requires or prolongs (>48 hours) inpatient hospitalization
- Is a persistent or significant disability or incapacity
- Is considered an important medical event\*

\*Important medical events may be considered serious by the investigator although they may not be immediately life threatening or result in death or prolong hospitalization. Such important medical events are those that may jeopardize the subject, require intervention to prevent one of the outcomes listed above, or result in urgent investigation. Examples include, but are not limited to, allergic bronchospasm, convulsions, and blood dyscrasias.

---

**Serious Adverse Events should be reported to the study Sponsor as soon as possible (24 hours recommended), but no more than 10 working days after the date the site becomes aware of the event.**

**Sites are also required to adhere to the reviewing IRB/EC requirements for reporting of SAE's.**

### ***6.13 Major Adverse Events (MAE)***

The following specific events will be considered major adverse events (MAE) for the purpose of evaluating the primary (30 day) and secondary (1 year) safety endpoints:

Major adverse events (MAE) are defined as any one of the following events:

- Death
- Myocardial Infarction
- Stroke (excludes TIA)
- Renal Failure (excludes renal insufficiency)
- Respiratory Failure (excludes COPD or pulmonary complications)
- Paralysis (excludes paraparesis)
- Bowel Ischemia
- Procedural Blood Loss ( $\geq 1,000$  cc)

A major adverse event (MAE) may or may not be considered related to the device. Mortality will be reported as “all cause” and “AAA related.” All deaths occurring in the first 30 days post-index procedure are considered “AAA related.”

The Clinical Events Committee (CEC) shall determine which adverse events are considered Major Adverse Events (MAE) for evaluation of the primary (30 days) and secondary (1 year) safety endpoints.

### ***6.14 Unanticipated Adverse Device Effect (UADE)***

An unanticipated adverse device effect means any serious adverse effect on health or safety or any life-threatening problem or death caused by, or associated with, a device, if that effect, problem, or death was not previously identified in nature, severity, or degree of incidence in the protocol or application (including a supplementary plan or application), or any other unanticipated serious problem associated with a device that relates to the rights, safety, or welfare of subjects.

**Unanticipated Adverse Device Effect (UADE) are to be recorded in the Adverse Event eCRF and the event is to be reported to the Sponsor within 24 hours of knowledge of the event. Sites are also required to adhere to the reviewing IRB/EC requirements for reporting of any UADE.**

### ***6.15 Conversion to Open Surgical Repair***

Conversion to open surgical repair may occur either at the initial implant procedure or subsequent to the initial procedure. Information regarding the surgical conversion will be recorded on the Procedure eCRF (if at initial implant) or Follow Up eCRF (after implant), and the **Adverse Event eCRF/ Secondary Intervention eCRF**.

In the event that a subject requires conversion from endovascular to open surgical repair, the explanted device should be sent to the Sponsor for examination. Refer to **Appendix VI** for specific instructions for managing the removal, shipping and handling of the explanted device. Explant information will be recorded on the **Secondary Intervention eCRF under Adverse Event eCRF**.

Surgical conversions must be reported by telephone, email or EDC system by noting an Adverse event/secondary intervention to the study Sponsor **within 24 hours** of knowledge of the event.

The Follow-up visit schedule for surgically converted subjects is at one month post open conversion.

#### **6.16 Technical Failures**

In the event that an AAA stent graft could not be deployed due to a technical failure, contact Clinical Affairs to obtain device return information. Device failure information will be captured on the **Procedure eCRF**.

#### **6.17 Deaths**

Any deaths that occur during the conduct of the study must be reported to the study Sponsor **within 24 hours** of becoming aware of the event. Sites are also required to adhere to the reviewing IRB/EC requirements for reporting of deaths. In addition, subjects with an implanted device who expire before completing the study should have the device explanted and sent to the Sponsor whenever possible for examination. Additional information to be submitted to the Sponsor may include such documents as: death certificate, autopsy report, summary of death report, hospital records, explant reports and copy of IRB/EC notification of the event. Patient death will have only one corresponding adverse event with outcome of “Death”, entered for the most proximal cause of death. Upon entry of the death into the **Study Exit eCRF**, every patient death will be determined to be “AAA-Related”, or “Non-AAA-Related”.

#### **6.18 Explants**

Specific instructions for managing the removal, shipping and handling of the explanted device can be found in **Appendix VI: Explant Procedure** and Manual of Operations. Explant information will be recorded on the **Adverse Event/Secondary Intervention eCRF**.

## 7.0 ENDPOINTS

### 7.1 *Primary Endpoint*

The primary objective of this study is to evaluate treatment success at 12 months with the Ovation Alto Abdominal Stent Graft System in subjects with AAA.

Treatment success will be a composite endpoint comprised of all of the following:

- Technical success\*;
- Freedom from type I & III endoleak at 12 months, to be assessed by an Independent Core Lab;
- Freedom from stent graft migration > 10 mm at 12 months (compared to 1-month baseline) , to be assessed by an Independent Core Lab;
- Freedom from AAA enlargement > 5mm at 12 months (compared to 1-month baseline);
- Freedom from AAA rupture through 12 months;
- Freedom from conversion to open repair through 12 months;
- Freedom from stent graft stenosis, occlusion, or kink requiring secondary intervention through 12 months;
- Freedom from thromboembolic event attributable to stent graft requiring secondary intervention through 12 months, and:
- Freedom from stent fracture requiring secondary intervention through 12 months

\*Technical Success will be a composite endpoint comprised of all of the following:

- Successful delivery, defined as ability to deliver the implant to the intended location without the need for unanticipated corrective intervention related to delivery, using an adjunctive device outside of the Ovation Alto Abdominal Stent Graft System;
- Successful and accurate deployment, defined as:
  - deployment of the endovascular stent graft in the planned location
  - patency of the endovascular stent graft, absence of device deformations (e.g. kinks, stent eversion, mal-deployment, misaligned deployment) requiring unplanned placement of an additional device within the endovascular stent graft, and;
  - successful withdrawal of the delivery system without the need for unanticipated corrective intervention related to withdrawal

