	
device within the endovascular stent graft, and;
 
 
• Successful withdrawal (i.e. successful withdrawal of the delivery system, without the need for unanticipated corrective intervention related to withdrawal)
 
 
Note: Unanticipated corrective intervention is unplanned implant of a third party device (outside of the Sponsor’s available device platform) to treat/exclude the aneurysm.
 
** Defined as deep vein thrombosis, pulmonary embolism, embolic stroke, limb ischemia in the presence of occlusion or thrombosis within the stent graft.

Additional Study Evaluation
	
Additional assessments that will be reported at each follow-up interval include:
 
 
• Type I, II, III and IV endoleaks and endoleaks of unknown origin, to be assessed by an Independent Core Lab
 
• Stent graft migration > 10 mm (compared to 1-month baseline), to be assessed by an Independent Core Lab
 
• AAA enlargement > 5 mm (compared to 1-month baseline), to be assessed by an Independent Core Lab
 
• AAA rupture
 
• Conversion to open repair
 
• Secondary interventions**
 
• AAA-related mortality**
 
• Device-related AEs & SAEs**
 
• Major Adverse Events (MAE)**
 
• Loss of patency
 
• Stent fracture, to be assessed by an Independent Core Lab
 
• Thromboembolic event (deep vein thrombosis, pulmonary embolism, embolic stroke, limb ischemia)
 
 
** MAEs and device-related SAEs will be adjudicated by the Clinical Events Committee (CEC) at 1, 6 and 12 months.
 
MAE is defined as:
 
 
• All-cause mortality
 
• Myocardial infarction
 
• Stroke (excludes TIA)
 
• Renal failure (excludes renal insufficiency)
 
• Respiratory failure (excludes COPD or pulmonary complications)
 
• Paralysis (excludes paraparesis)
 
• Bowel ischemia
 
• Procedural blood loss (≥1,000 cc)
 

Subject Enrollment
	
Patients with AAA will be prospectively enrolled and treated with the Ovation Alto Abdominal Stent Graft System. Treatment

	success at 12 months will be compared to a performance goal of 80%.

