## 1.0 STUDY GOAL AND OBJECTIVES

The goal of the study is to evaluate the Ovation Alto Abdominal Stent Graft System in subjects with abdominal aortic aneurysm (AAA). The primary study objective is to evaluate treatment success at 12 months in patients treated with Ovation Alto relative to a performance goal of 80%.

Treatment success will be defined as:

- Technical success\*
- Freedom from type I & III endoleaks at 12 months
- Freedom from stent graft migration > 10 mm at 12 months (compared to 1-month baseline)
- Freedom from AAA enlargement > 5mm at 12 months (compared to 1-month baseline)
- Freedom from AAA rupture through 12 months
- Freedom from conversion to open repair through 12 months
- Stent graft stenosis, occlusion or kink requiring secondary intervention through 12 months
- Thromboembolic event\*\* attributable to stent graft requiring secondary intervention through 12 months
- Stent fracture requiring secondary intervention through 12 months

\*Technical Success is defined as:

- Successful delivery (i.e. ability to deliver the implant to the intended location site without the need for unanticipated corrective intervention related to delivery, using an adjunctive device outside of the Ovation Alto Abdominal Stent Graft System);
- Successful and accurate deployment, defined as:
  - deployment of the endovascular stent graft in the planned location;
  - patency of the endovascular stent graft, absence of device deformations (e.g. kinks, stent eversion, mal-deployment, misaligned deployment) requiring unplanned placement of an additional device within the endovascular stent graft, and
- Successful withdrawal (i.e. successful withdrawal of the delivery system, without need for unanticipated corrective intervention related to withdrawal).

Note: Unanticipated corrective intervention is unplanned implant of a third party device (outside of the Sponsor's available device platform) to treat/exclude the aneurysm.

\*\* Defined as deep vein thrombosis, pulmonary embolism, embolic stroke, limb ischemia in the presence of occlusion or thrombosis within the stent graft.

Additional assessments that will be reported at follow up include:

- Type I, II, III and IV endoleaks and endoleaks of unknown origin
- Stent graft migration > 10 mm (compared to 1-month baseline; assessed at 6-months)

- AAA enlargement > 5 mm (compared to 1-month baseline; assessed at 6-months)
- AAA rupture
- Conversion to open repair
- Secondary interventions\*\*\*

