### 6.1 *Endoleak*

Endoleak is evaluated by the Independent Core Lab and is defined by the persistence of blood flow outside the lumen of the endovascular graft but within the aneurysm sac and can be classified as:

- *Type I* – Ineffective seal at either the proximal or distal sealing zones
    - *Type IA* – Ineffective seal at the proximal sealing zone
    - *Type IB* – Ineffective seal at the distal sealing zone
  - *Type II* – Retrograde blood flow from lumbar arteries, the inferior mesenteric artery, or other collateral vessels into the aneurysm sac
  - *Type III* – A leak caused by fabric tears or disruption, component disconnection, or graft disintegration
  - *Type IIIA* - Junctional leak or component disconnection
  - *Type IIIB* - Midgraft hole
  - *Type IV* – Blood flow through an intact fabric.
  - *Unknown endoleak* - Endoleak present but unable to assess type
- Endoleak will only be evaluated as an adverse event or serious adverse event if it is present at the 30-day follow-up visit or if a post-index procedure re-intervention occurs.

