### 7.2 *Additional Study Evaluation*

Additional assessments that will be reported at each follow-up interval include:

- Type I endoleak, to be assessed by an Independent Core Lab
- Type III endoleak, to be assessed by an Independent Core Lab
- Stent graft migration > 10 mm (compared to 1-month baseline), to be assessed by an Independent Core Lab
- AAA enlargement > 5 mm (compared to 1-month baseline)
- Loss of patency
- Stent fracture, to be assessed by an Independent Core Lab
- AAA rupture
- Conversion to open repair

- Secondary interventions
- AAA-related mortality
- Adverse events, including:
  - Serious adverse events
  - Major adverse events
  - Procedure-related adverse events
  - Device-related adverse events
  - All adverse events, regardless of seriousness or cause

All deaths that occur in the study will be adjudicated by the CEC. AAA related death is any death determined by the CEC to occur as a result of the initial procedure (first 30 days), AAA rupture, conversion to open surgical repair, or any AAA related secondary intervention.

---

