## 8.0 DATA ANALYSIS

### 8.1 *Analysis Population*

Primary analyses will be performed on a modified intent-to-treat basis. The modified intent-to-treat group includes all subjects in which the delivery system was inserted into an access vessel. All subjects who achieve technical success and remain free of all other elements of the composite effectiveness endpoint at 12 months will be considered treatment successes. All subjects who fail based on any element of the composite effectiveness endpoint, and all subjects who deemed treatment successes will be included in the denominator. Only subjects with readable imaging during each respective follow-up interval will be included in the denominator for relevant effectiveness endpoints. Subjects not counted as failures, but with incomplete data to assess all the composite elements will be treated as missing data points.

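### Does the primary endpoint need a stated score for an untyped endoleak at 12 months, and a re-scoring of Type I/III leaks repaired earlier?

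*Combined protocol and SAP*

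**What the plan says.** The Protocol Summary, 1.0 and 7.1 all judge endoleak by its status at 12 months. Section 1.0 has "Freedom from type I & III endoleaks at 12 months", and 7.1 has "Freedom from type I & III endoleak at 12 months, to be assessed by an Independent Core Lab". Other elements are cumulative, for example "Freedom from stent graft stenosis, occlusion, or kink requiring secondary intervention through 12 months". Thromboembolic events and stent fractures requiring secondary intervention, rupture and open conversion are cumulative too.

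Section 6.1 lists Types I to IV and an unknown class, defined as "Endoleak present but unable to assess type". It says that an endoleak is evaluated as an adverse event only "if it is present at the 30-day follow-up visit or if a post-index procedure re-intervention occurs".

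Section 8.1 says that subjects with technical success who "remain free of all other elements of the composite effectiveness endpoint at 12 months will be considered treatment successes". Subjects who fail any element are in the denominator. Those who have not failed, but lack the data to assess every element, are treated as missing. Section 8.3 repeats this, promises sensitivity analyses for missing data, and leaves the complete methods to a prospectively written SAP, whose text is not in the combined document.

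For descriptive reporting, the Summary lists "Type I, II, III and IV endoleaks and endoleaks of unknown origin, to be assessed by an Independent Core Lab", and 1.0 lists the same classes. Section 7.2 opens with "Additional assessments that will be reported at each follow-up interval include" and then names only Type I and Type III among the endoleaks. Both the Summary and 7.2 list secondary interventions.

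**The concern.** Two things look wrong on a first reading.

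**Untyped leak.** A leak of unknown type may be Type I or III. Under 7.1 alone it could pass as a success, because no Type I or III leak has been shown. Under 8.1 it could be missing. Neither reading counts it as a failure on the endoleak element. The readable-imaging sentence in 8.1 does not settle the matter, since a scan can be readable and still leave the type open. Section 5.5.1.5 also allows duplex ultrasound with non-contrast CT when contrast is not tolerated. In a single-arm trial judged against a fixed 80% goal, an open score for part of the primary endpoint could decide a close result.

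**Repaired leak.** A re-intervention for stenosis, kink, thromboembolism or fracture fails the subject whenever it happens in the first year. A re-intervention for a Type I or III leak does not, provided that the leak is gone at 12 months. Counts by interval show that repairs took place, but not how many treatment successes depended on one.

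**Working it through.** **Inputs.** From 8.4 and 8.5: goal 80%, assumed success 92.8%, one-sided exact 95% lower limit, 60 evaluable subjects, up to 75 enrolled, stated power 86.1%. The documents give no rate for untyped or repaired leaks, so any such rate below is an assumption.

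**Formulas.** With x successes in n, the lower limit L(x, n) is the 5th percentile of a Beta(x, n − x + 1) distribution. The endpoint is met if L > 0.80. The smallest passing count c(n) is the smallest r with P(X ≥ r | n, 0.80) ≤ 0.05.

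**Step 1: the plan's own figure.** At n = 60, P(X ≥ 54 | 0.80) = 0.0308 and L(53, 60) = 0.7920, so c(60) = 54. Power is P(X ≥ 54 | 60, 0.928) = 0.8611, which reproduces 86.1%.

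**Step 2: one untyped leak at n = 60, with six other failures.**

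| Score of the untyped leak | Count | Lower limit | Goal met |
|---|---|---|---|
| Success | 54/60 | 0.8121 | yes |
| Missing | 53/59 | 0.8091 | yes |
| Failure | 53/60 | 0.7920 | no |

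The success and missing scores agree. They also agree at n = 60 with two or three untyped leaks: with six other failures the limits are 0.8121 and 0.8060 for two leaks, and 0.8121 and 0.8028 for three. The failure row carries little information. It starts from the smallest passing count, so taking away one success must miss the goal.

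**Step 3: other sizes from 60 to 75.** For one leak, the success and missing scores can differ only where c(n) = c(n − 1). That happens twice: c(62) = c(63) = 56 and c(68) = c(69) = 61.

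| n | Success | Missing |
|---|---|---|
| 63 | 56/63, L = 0.8014 (met) | 55/62, L = 0.7984 (not met) |
| 69 | 61/69, L = 0.8005 (met) | 60/68, L = 0.7977 (not met) |

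Two leaks add n = 64 and 70; three add n = 65 and 71.

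**Step 4: how often.** If the true rate is 92.8%, P(X = 56 | 63) = 0.0845 and P(X = 61 | 69) = 0.0633. The scores conflict only if at least one of those successes also has an untyped leak. If 1% of successes do (assumed), the joint chances are:

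- n = 63: 0.0845 × (1 − 0.99^56) = 0.0845 × 0.430 = 3.6%
- n = 69: 0.0633 × (1 − 0.99^61) = 0.0633 × 0.458 = 2.9%

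At an assumed 2% they are 5.7% and 4.5%. Each figure applies only if the evaluable number turns out to be exactly 63 or 69.

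**Step 5: which reading the text supports.** Section 6.1 defines the class by the inability to assess type. The endoleak element needs the type. Sections 8.1 and 8.3 make a subject who has not failed, and whose data cannot settle every element, missing. The general rule therefore covers the case, and the sensitivity analyses promised in 8.3 then apply. Such a subject can still fail on enlargement, rupture, conversion or another element.

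**Step 6: repaired leaks.** Near the assumed rate, 56/60 has L = 0.8539. Moving one, two or three subjects to failure gives 55/60, 54/60 and 53/60, with limits 0.8327, 0.8121 and 0.7920. At assumed repair rates of 1%, 2%, 3% and 5%, the chance of three or more repaired subjects in 60 is 2%, 12%, 27% and 58%, if every one of them was otherwise a success. Those limits answer a different question from the one the plan poses. The 92.8% in 8.5 came from applying this study's success definitions to the earlier Ovation IDE data, so the assumption and the endpoint match.

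**The case for a change.** The strongest case for a change is that the score of any primary component should be fixed before data are seen, that one sentence would do it, and that the conflict in scores at n = 63 and n = 69 is real and within the planned range. The sensitivity analyses in 8.3 would not reach an untyped leak that had been read as a success. For repaired leaks, a per-subject count would use data already collected and would show what interval totals cannot.

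What stands is that no section names the untyped leak in the composite, and that the list in 7.2 is shorter than those in the Summary and 1.0. The mismatch affects only descriptive reporting.

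The rest carries less weight. That the score would be chosen after the results are known is an inference: 8.3 commits to a prospective SAP, and its absence from the combined document does not show that the rule is absent. The most that could be asked is confirmation of the reading that 8.1 already supports. For repaired leaks, the endoleak element is worded alike in the Summary, 1.0 and 7.1. Type I and III leaks and secondary interventions are already reported at each interval. Section 6.11 counts events resulting from intervention on the aneurysm or device as device-related, and 11.2 sends device-related events to the Clinical Events Committee. A further descriptive figure would change no result.

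**Conclusion.** No change follows. The untyped leak is a gap in detail that an analyst fills from the general rule in 8.1 and 8.3: the subject is missing unless another element has failed, and the missing-data sensitivity analyses apply. At the planned 60 evaluable subjects this gives the same verdict as scoring the leak a success. For one leak, the two scores part only at n = 63 and n = 69 with the success count exactly on the boundary, a joint chance of about 3% to 6% at those sizes if 1% to 2% of successes have an untyped leak. That percentage is an assumption. The shorter list in 7.2 is a clerical mismatch with no effect on the test.

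Judging endoleak at 12 months, so that a repaired leak can still be a success, is a fair and consistent choice. It matches the derivation of 92.8% and leaves the 86.1% power and the sample of 60 intact. Repairs remain visible in the interval reports. A supportive per-subject count would be optional, with no bearing on whether the 80% goal is met. This conclusion rests on the combined document alone; the SAP announced in 8.3 could not be checked.
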